1. PURPOSE OF STUDY

This study represents the third phase of a larger research project developed for a U01 award as part of the Collaborative Initiative on Fetal Alcohol Spectrum Disorders (CIFASD) funded by the National Institute on Alcohol Abuse and Alcoholism (NIAAA). The overall project aims to develop and evaluate a mobile health (mHealth) application (app) for parents/caregivers of children with fetal alcohol spectrum disorders (FASD). The primary focus of the FMF Connect app is to provide parent/caregiver education and support.

The first phase of this project was approved under IRB protocol #1266 (legacy RSRB#67394). In that phase we used qualitative research methods to engage parents and caregivers in the development of the mHealth intervention and obtain iterative feedback on acceptability and feasibility. A prototype of the app was developed in both iOS and Android and beta-testing was completed with parents/caregivers and providers. In the second phase of the study, we conducted a feasibility trial of the FMF Connect app with parents/caregivers under IRB protocol #4433. This included quantitative pre-post surveys and qualitative interviews with a subsample of users to optimize the intervention and trial procedures. In this third phase, we will conduct a larger scale randomized controlled trial (RCT) to test the efficacy of the FMF Connect app for parents/caregivers of children with FASD. We hypothesize that participants who receive the FMF Connect app (with or without the additional Coaching Module) will have improve outcomes relative to the waitlist control group. We anticipate the Coaching Module will increase participant engagement and usage of the FMF Connect app. Finally, we hypothesize that parental attributions of behavior targeted by the FMF Connect app will mediate intervention effects on child behavior and parenting self-efficacy.

2. BACKGROUND AND RATIONALE

Children with fetal alcohol spectrum disorders (FASD) have significant neurobehavioral impairments that contribute to poor adaptive function and increased behavior problems in home, school, and community settings [1]. Most interventions for preschool and school-aged children with FASD, the largest age group with identified FASD [2], are directed at caregivers or have included parent training to facilitate child skill acquisition [3]. Interventions directed toward caregivers are an essential component of FASD integrated care models [3,4]. Tailored FASD-informed caregiver interventions provide families with the knowledge and skills to better understand their children's development and behavior, generate effective environmental accommodations and behavior plans, teach and generalize targeted child skills, and advocate for their children in school and community settings [3]. These strategies are vital for sustained child improvement and better family adaptation.

Unfortunately, we and others have documented that the vast majority of families cannot access FASD-informed interventions. Barriers to care occur because a knowledgeable and skilled workforce is lacking [5,6], and there are family-level barriers such as limited financial resources, inability to access childcare, and stigma [7]. Access to appropriate FASD-informed care is even more limited in less densely populated areas. Many families try peer-to-peer and self-help strategies, but it can be difficult to evaluate the credibility and effectiveness of information provided through these modalities.

The primary objective of this project is to develop and evaluate an mHealth app to directly provide caregivers with evidence-based content and peer-moderated support they can easily access and use to improve outcomes for their children and families. The app, called “FMF Connect,” is derived from our work on the scientifically-validated Families Moving Forward (FMF) Program that has shown promising results for child and caregiver outcomes in three trials with families raising children with FASD [8]-[10].

This project follows a systematic approach to the development and evaluation of the FMF Connect mHealth intervention. The app is designed for use by caregivers, utilizes a cloud-based infrastructure, and builds on our existing open source framework for the development of medical apps [11], and those of others [12,13]. Feasibility tests and iterative feedback from diverse caregivers have aided in fine tuning caregiver instructions, content, and user-interface features throughout the development process.

The proposed RCT will establish the efficacy of the FMF Connect mHealth intervention in a large-scale efficacy trial. It will also assess the patterns of app usage that relate to the greatest improvements in child and caregiver outcomes and test whether text-based coaching increases engagement with the app. Consistent with prior FMF trials, targeted outcomes include satisfaction, child behavior problems, caregiver FASD/advocacy knowledge, attributions of misbehavior, parenting practices, parenting efficacy, self-care, and social support. This novel mHealth intervention has the potential to reach many families in need and reduce significant barriers to care, resulting in broader public health impact.

3. ADMINISTRATIVE ORGANIZATION

This study will be conducted through the University of Rochester (UR) and will involve faculty, students, and staff within the following departments and centers: Department of Psychology, Mt. Hope Family Center (MHFC; which is a part of the Psychology Department), Department of Electrical and Computer Engineering (ECE). [name] primary appointment is at MHFC and the Psychology Department. She oversees the study coordinator, research assistant, and graduate and undergraduate students working on the project within these departments. [name] is faculty within ECE and oversees staff and students within these departments contributing to the project. Weekly project lab meetings ensure coordination across all aspects of the project.

All data collection and communication with participants is completed by UR project staff. Consenting and screening data, contact information, and quantitative survey pre-post data will be collected and stored online using REDCap hosted by UR. Participant interaction with the app is recorded using Amazon Web Services (AWS; HIPAA-Compliant). All paper and electronic files will be securely stored on MHFC servers and in locked cabinets only accessible to UR project staff.

As part of CIFASD, this study may involve data sharing as outlined by the policies and procedures established by CIFASD and required by NIAAA: <https://cifasd.org/data-sharing/>. De-identified data will also be stored in the CIFASD Central Repository hosted at Indiana University (IU), as is required by NIAAA for all projects involved in CIFASD.

4. STUDY DESIGN

This study involves a three arm RCT with equal allocation to the following conditions: (1) FMF Connect + coaching, (2) FMF Connect alone, and (3) waitlist control. Quantitative survey data will be collected at three timepoints: baseline (T1), 6-weeks (T2), and 12-weeks (T3). The T2 timepoint will involve an abbreviated battery designed to allow statistical tests of mediation hypotheses (see Data Analysis Plan below). Primary study outcomes include child behavior, parent FASD knowledge,

parenting self-efficacy, behavior attributions, family needs met, and parent use of self-care. We are also interested in participant ratings of app quality and patterns of app usage. App usage will be recorded through AWS during the study period. After T3, study participants in the waitlist control group will receive the FMF Connect app.

5. SUBJECT POPULATION

The subject population will include parents and caregivers of children (ages 3-12) with fetal alcohol spectrum disorders (FASD) or affected by prenatal alcohol exposure (PAE) who live in the United States.

We are aiming to include 150 parents or caregivers with usable data in this study to achieve adequate power for study aims (see data analysis section below). We expect a portion of families will enroll in the study, but not complete assessments or install the app. Based on our feasibility trial, 57% of participants who initiated screening were eligible for the study and had complete data. This percentage may be a bit lower than we can achieve for the proposed RCT given that the COVID-19 pandemic began right after the initiation of the feasibility trial and affected participation. We also identified some inefficiencies in our enrollment process that we can improve to reduce incomplete data. Of eligible families selected for the study, we expect about 85% of eligible families to complete baseline surveys. Of these families, about 80% are likely to install and use the app at least once. To attain our desired sample size, we will aim to enroll about 300 parents and caregivers.

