9. STUDY PROCEDURES

Data Collection & Randomization Procedures

Parents/caregivers who are eligible for the study will be sent an email inviting them to complete the baseline study surveys (see survey battery below) administered by REDCap. Participants will be

asked to enter their zip code to verify their identity when completing baseline and follow-up surveys (this will be verified against value entered in demographic surveys in the screening module). Families deemed ineligible after detailed review will be informed of their status.

Following baseline survey completion, participants will be randomized to one of three arms of the RCT:

1. FMF Connect app + text based coaching (within the app)
2. FMF Connect app (without coaching)
3. Waitlist control

Randomization will occur through the REDCap Randomization module, with an equal allocation pattern across groups. Participants will be notified of their group status via email. Emails for parents/caregivers in either of the FMF Connect app intervention groups (groups 1 and 2) will also include instructions of how to install the FMF Connect app on their devices. The email for the parents/caregivers in the FMF Connect app + coaching group (group 1) will inform them that they will receive an introductory email from their assigned coach in the next few days. Details about the FMF Connect app and Coaching interventions and described below.

All participants regardless of group assignment will receive emails through REDCap at 6 weeks and 12 weeks inviting them to complete follow-up surveys, along with a personalized link (see survey battery below). The assessment battery is estimated to take 35-45 minutes to complete at T1 and T3; T2 is estimated at 15-20 min. Waitlist control participants will receive the FMF Connect app following T3 survey completion.

Measure	Baseline (T1)	6-Weeks (T2)	12-Weeks (T3)
Eyberg Child Behavior Inventory (5-8min)	X		X
Reasons for Children’s Behavior Scale (4-6min)	X	X	X
Everyday Life Scale (4-6min)	X	X	X
Parenting Sense of Competence Scale (3-5min)	X	X	X
Family Needs Questionnaire (3-5min)	X		X
Knowledge & Advocacy Questionnaire (15-20min)	X		X
Self-Care and Support Assessment (3-5min)	X		X
Adverse Childhood Experiences (2 min)	X		
Family Background & Services Survey (5-10min)	X		X
COVID-19 Experiences Survey (5 min)			X
User Version of the Mobile Health Application Rating Scale (5-8min)			X

FMF Connect mHealth Intervention

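### Does the 80% app-install rate in Section 5 remove non-installers from the analysis, although the waitlist cannot install before T3?

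*Combined protocol and SAP*

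**What the plan says.** Section 5 states the target: "We are aiming to include 150 parents or caregivers with usable data in this study to achieve adequate power for study aims". It then explains why more must be enrolled: "We expect a portion of families will enroll in the study, but not complete assessments or install the app". Two rates follow. The first is "Of eligible families selected for the study, we expect about 85% of eligible families to complete baseline surveys"; the second is "Of these families, about 80% are likely to install and use the app at least once". The paragraph ends with an enrolment aim of about 300. It does not multiply the rates out, give a T3 completion rate, or define usable.

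On timing, Section 9 says "Following baseline survey completion, participants will be randomized to one of three arms of the RCT", and Section 4 says "After T3, study participants in the waitlist control group will receive the FMF Connect app". On follow-up, Section 9 says "All participants regardless of group assignment will receive emails through REDCap at 6 weeks and 12 weeks" to complete surveys. Section 14 lets caregivers leave the app unused and says the team still wants survey data from people who did so. In Section 19, Aim 2 compares families by the arm to which they were randomised. Aim 1 compares app usage between the coaching arm and the app-alone arm. Neither aim is restricted to installers, and neither carries an explicit intention-to-treat statement.

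**The concern.** Section 5 puts failure to install the app beside failure to complete assessments, as if both made a caregiver unusable. It then applies the install rate to a group that includes the waitlist, whose members have nothing to install until the comparison is over.

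If usable did mean installed, the filter would act after randomisation and in the app arms only. Aim 2 would then compare self-selected installers with an unselected waitlist, and the bias could go either way.

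The coaching contrast in Aim 1 would have a related weakness. The coaching arm's allocation notice "will inform them that they will receive an introductory email from their assigned coach in the next few days", so contact with a coach may come before installation. A comparison of installers alone would miss any effect of coaching on whether the app is installed at all.

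**Working it through.** **1. Does the 80% lead to the plan's own figure?**

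Inputs, all from Section 5: about 300 enrolled, 150 usable, 57% feasibility yield, 85% baseline completion, 80% install and use. Yield = 300 × the rates applied; enrolment needed = 150 / the rates applied.

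| Rates applied | Yield from 300 | Enrolment needed for 150 |
|---|---|---|
| 57% | 171 | 263 |
| 85% | 255 | 176 |
| 85% × 80% | 204 | 221 |
| 57% × 85% | 145 | 310 |
| 57% × 85% × 80% | 116 | 387 |

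No row turns 300 into 150. The closest, 57% × 85%, counts a loss twice, because the 57% already requires complete data. The 80% therefore cannot be shown to be a working step in the sample-size arithmetic. Getting from 204 to 150 needs a further retention of 150/204 = 73.5%, which is not stated.

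**2. What changes if the 80% is limited to the app arms?**

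Assume that the 300 are eligible enrollees. Then 300 × 0.85 = 255 are randomised, or 255/3 = 85 per arm, and 85 × 0.80 = 68 install in each app arm.

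- 80% for everyone, as worded: 255 × 0.80 = 204.
- 80% in the app arms only: 68 + 68 + 85 = 221.
- No install step: 255.

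T3 completion is not given, so a range is shown as an assumption:

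| T3 completion | 80% for all | 80% in app arms | No install step |
|---|---|---|---|
| 70% | 143 | 155 | 179 |
| 80% | 163 | 177 | 204 |
| 90% | 184 | 199 | 230 |

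The completion needed for 150 is 150/204 = 74%, 150/221 = 68% and 150/255 = 59%. The uniform rate is the most demanding of the three, so correcting it can only raise the expected yield.

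**3. Does any text set up the filter?**

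- Section 5 forecasts losses and states no analysis set. Elsewhere in the same paragraph the feasibility yield counts people with complete data, and the enrolment improvements are aimed at incomplete records. In that setting, usable most naturally means adequate survey data.
- Section 9 surveys all arms. Section 14 wants non-users' surveys. Section 19 frames Aim 2 by randomised arm.
- Section 19 uses 100 caregivers for the two app arms (50 each) and 150 for three arms (150/3 = 50 each). An install filter in the app arms alone would split 150 as about 150 × 68/221 = 46, 46 and 150 × 85/221 = 58. The equal 50s fit an analysis without such a filter. They do not prove it, because a uniform discount would also leave equal arms.

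**4. The coaching contrast.** Section 19 asks whether usage is higher in one randomised arm than in the other. Usage is logged automatically (Section 4). A caregiver who never installs has used the app zero times, so the natural analysis of the stated question already includes them.

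**The case for a change.** The best case for a change is that Section 5 is the only place where installation is tied to the analysable sample, and it leans towards exclusion. The passages on the other side are not analysis rules. Section 9 says who is surveyed, Section 14 wants non-users' views largely to improve the app, and Section 19 names a comparison without saying who stays in it. Two readings of one plan leave room to choose after results are seen. On the assumption in step 2, the filter would remove 85 − 68 = 17 caregivers from each app arm, 34 in all, and none from the waitlist. A few sentences would settle it.

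Part of this stands. Usable is undefined, the 80% is worded too broadly, and an explicit as-randomised statement would be tidier. But the harm requires analysts to adopt a rule nobody wrote, against the direction of three sections. The size of any bias cannot be worked out, because the documents give no prognostic difference between installers and non-installers and no effect of coaching on installation. Nor would a definition of usable deal with non-installers who also skip T3. That is a question of missing follow-up data, and it exists whatever Section 5 says about installation.

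**Conclusion.** The inconsistency is real but minor: a usage forecast for the app arms is worded as if it covered the waitlist. Followed as written, the plan surveys everyone, compares randomised arms in Aim 2 and compares usage between the two randomised app arms in Aim 1. No stated figure depends on the 80%, and narrowing it moves the expected yield from 204 to 221 before T3 loss, in the favourable direction.

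The finding that these yields exceed 150 before T3 loss rests on enrolled meaning eligible enrollees. Section 7 also uses the word for families entering the consent and screening module. On that reading 300 × 0.57 = 171 would have complete data, still above 150, provided that the feasibility yield holds and the 85% is not applied again on top of it. This is a gap in wording that analysts can be expected to fill sensibly, and no change to the plan is needed.

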6. INCLUSION AND EXCLUSION CRITERIA

Inclusion criteria:

- Biological parent or other primary caregiver (e.g., foster or adoptive parent, relative, legal guardian) of a child with FASD or PAE
- The parent/caregiver must be at least 18 years old
- The child must be between the ages of 3 and 12 years old (if there is more than one child in the family with FASD/PAE in this age range, the parent/caregiver is instructed during screening to choose one to complete study surveys about)
- The child has a diagnosis of FASD or has confirmed PAE
- The child has lived with the parent/caregiver for at least 4 months and is expected to remain in the home for at least 1 year
- The parent/caregiver lives in the United States
- The parent/caregiver has a smartphone or iPad with iOS operating system

Exclusion criteria:

- The parent/caregiver is not fluent in English (the FMF Connect app and pre-post measures are currently only available in English)
- There is another parent/caregiver of the same child or living in the home that is already enrolled in the study (couples are excluded to prevent dependence in the data)
- The parent/caregiver participated in a prior trial of the FMF Connect app as part of phase 1 or 2 of this project.
- The family has previously received or is currently receiving the therapist-led Families Moving Forward (FMF) Program

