7. RECRUITMENT METHODS

Potential participants will be recruited through a variety of mechanisms, consistent with previous studies in our research group and in CIFASD. The Study Website will include information about the study, as well as a link to the study REDCap Consenting and Screening Module for interested families to enroll.

The following materials have been developed to aid with recruitment: (1) study flyers, (2) social media banners formatted for Facebook, Twitter, and Instagram, and (3) powerpoint slide. Information about the study will be disseminated in various ways:

- [name] will share study recruitment materials with providers and community advocates who regularly see children with FASD
- We will post study information on our study Twitter account (@FMFConnect) and newsletter (www.fmfconnect.com)
- CIFASD investigators can inform research participants or patients in their local sites or clinics for which they have routine access
- The National Organization on Fetal Alcohol Syndrome (NOFAS) is a member of CIFASD and has a mission to educate the public about FASD and disseminate research and policy information. They can disseminate the study flyer through their Weekly Round-Up newsletter, significant social media presence, and to their state and local affiliates who can share in their communities
- [name] and other CIFASD investigators may include slides about the study in conference or community presentations
- Organizers/moderators of popular social media groups can be sent recruitment materials and can choose to share with their members

As part of CIFASD, we will also try to aid other projects with recruitment from our study sample. Our Consenting and Screening Module includes a question asking if participants are interested in learning about other studies. For those that indicate yes, we will send them any new relevant flyers or information about other consortium projects they might be eligible for. We will submit any flyers and email language in a modification to this study prior to sending to our participants. For example, the DiG Human Genetics Study within CIFASD has previously referred some families to our study. We would like to send their study flyers (see attached flyer and email language) to participants in our sample who indicated they have not previously done the DiG study (in Screening Module).

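### The prior-exposure rule for the FMF Connect app applies to the individual caregiver, not the household, so a co-parent of a phase 1 or 2 app user can be randomised (minor)

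*Combined protocol and SAP*

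**What the plan says.** Section 6 of the protocol (Inclusion and Exclusion Criteria) lists three related exclusions, each with a different unit.

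- Concurrent enrolment, by child or home: "There is another parent/caregiver of the same child or living in the home that is already enrolled in the study". The reason given is that "couples are excluded to prevent dependence in the data".
- Earlier app trials, by individual caregiver: "The parent/caregiver participated in a prior trial of the FMF Connect app as part of phase 1 or 2 of this project".
- The therapist-led program, by family: "The family has previously received or is currently receiving the therapist-led Families Moving Forward (FMF) Program".

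Section 1 describes both earlier phases as putting the app in caregivers' hands. In phase 1, "beta-testing was completed with parents/caregivers and providers"; in phase 2, "we conducted a feasibility trial of the FMF Connect app with parents/caregivers". Section 2 states that the app is derived from the therapist-led program. Section 4 names child behavior and family needs met among six primary outcomes. Section 7 includes the project's own channels in recruitment: "We will post study information on our study Twitter account (@FMFConnect) and newsletter".

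**The concern.** The plan treats a family's earlier contact with the parent program as disqualifying, but applies a narrower rule to the app under test and gives no reason for the difference. A home where one caregiver worked through the app in phase 1 or 2 may already have changed how it manages the child. If the other caregiver enrols and is assigned to waitlist, that home is not a fully untreated control. If assigned to an app arm, it may have less left to gain. Either way the difference between app and waitlist shrinks, chiefly on outcomes that describe the child or the home rather than the respondent.

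**Working it through.** **1. Reading the rules together.** Take a caregiver whose partner was in the phase 2 feasibility trial and who did not take part personally.

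- Concurrent-enrolment rule: not triggered, because the partner is not in this study.
- Prior-app rule: not triggered, because this caregiver did not participate.
- Therapist-led rule: not triggered, because it concerns a different program.

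No other criterion in section 6 addresses earlier app use, so the caregiver is eligible as written.

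**2. The plan's own power figure.** Section 19, Aim 2, gives N = 150, 3 time points, correlation ρ of .3 to .5, α = .05 and f = .175, with power .87 to .96. For the group-by-time interaction with k = 3 groups and m = 3 time points:

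- λ = f²·N·m/(1−ρ), df = (k−1)(m−1) = 4 and (N−k)(m−1) = 294.
- ρ = .3: λ = .030625 × 450/.7 = 19.69, power .958.
- ρ = .5: λ = .030625 × 450/.5 = 27.56, power .994.

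The stated range is not reproduced. An f of .15, which the plan does not state, gives .873 to .963. The mismatch is conservative for this test and separate from the eligibility point, so both values of f are carried forward.

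**3. Effect of exposed homes.** Let p be the share of randomised homes with earlier app use. The documents give no value, so p is an assumption. As a worst case, let the arm difference in those homes be zero. The effect then becomes f(1−p), equivalent to keeping (1−p)² of the sample.

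| p | homes of 150 | (1−p)² | power from f = .175 (ρ .3 / .5) | power from f = .15 (ρ .3 / .5) |
|---|---|---|---|---|
| 0 | 0 | 1 | .958 / .994 | .873 / .963 |
| 2% | 3 | .960 | .950 / .992 | .857 / .956 |
| 5% | 7.5 | .9025 | .936 / .988 | .832 / .943 |
| 10% | 15 | .81 | .906 / .977 | .784 / .914 |

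At p = 2% the loss is 0.8 and 0.2 points from the stated f, and 1.6 and 0.7 points from f = .15.

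**4. Outcomes measured twice.** The survey table in section 9 gives the Eyberg inventory and the Family Needs Questionnaire at T1 and T3 only. With m = 2 and df = 2 and 147, f = .175 gives .905 / .974. At p = 2%, f = .1715 and λ = .02941 × 300/(1−ρ) = 12.61 / 17.65, with power .893 / .969. The loss is still about 1 point.

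**The case against.** The case for leaving the text alone has real force.

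- **Exposure of the co-parent is not shown.** Under section 10, app content sits behind a passcode or biometric lock and each caregiver has a separate username. A partner's past account does not prove that the co-parent used it. This stands as a reason to expect a small effect.
- **Most primary outcomes belong to the respondent.** FASD knowledge, self-efficacy, attributions and self-care can still improve in someone who never used the app. This stands too, and makes zero residual effect a worst case.
- **Reach is inferred.** Section 7 does not say who follows the Twitter account or receives the newsletter. That they reach former participants' homes is plausible but not documented.

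A reader might also infer more than the text supports.

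- *That homes can gain prior exposure through this trial.* The same-child, same-home exclusion largely closes that route. Its purpose, avoiding dependent data, applies equally to a partner who has finished or left, and section 14 allows withdrawn participants' data to be analysed. What remains is that the rule does not define when someone counts as enrolled.
- *That naming only phases 1 and 2 leaves a gap.* Section 1 says "This study represents the third phase of a larger research project", so those are all the earlier phases.
- *That the same caregiver can readily re-enter after a waitlist assignment.* Section 8 collects name, date of birth, contact information, identifier variables and IP address, and the coordinator reviews each record. The criteria do not spell out a bar on re-entry, but this is a minor ambiguity of wording.

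**Conclusion.** The gap is real but narrow: the app exclusion works at the individual level where the plan's own rule for the parent program works at family level. Severity is minor. The expected consequence is slight attenuation of the app-versus-waitlist contrast, mainly on child- and home-level outcomes. It should not be read as bias favouring an arm, because randomisation balances earlier exposure in expectation.

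The size cannot be determined from the documents. A loss of about a point of power or less at the stated effect size rests on an assumed 2% of homes and no remaining effect in them. A materially larger loss would need something like 10% of homes, and nothing in the documents suggests that share.

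**What to change.** Reword the prior-app exclusion in section 6 along these lines: *The parent/caregiver, or another parent/caregiver of the same child or living in the home, used the FMF Connect app in a prior trial as part of phase 1 or 2 of this project.* Tying it to use of the app matters. Section 1 says phase 1 also gathered qualitative input, and households that gave input without receiving the app should stay eligible.

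In the concurrent-enrolment rule, state that already enrolled means ever enrolled, including people who completed or withdrew.

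Make sure that screening asks about app use by anyone in the household; the Screening Form is not part of the document reviewed, so it may already do so. Have the coordinator check contact information against prior-phase records before the baseline invitation. A personal identifier alone would not link two caregivers in one home.

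The cost is two sentences, possibly one REDCap question, a record check for each applicant, and the loss of a few otherwise eligible co-parents. Treatment and analysis are unchanged.
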